3.0 LIST OF ABBREVIATIONS

AE	adverse event
ACR	American College of Rheumatology
ALT	alanine aminotransferase
Anti-dsDNA	antibody to double-stranded DNA
AST	aspartate aminotransferase
AUC(0-168)	area under the plasma concentration-time curve from time 0 to 168 hours postdose
AUC(0-t)	area under the plasma/blood/serum concentration-time curve from time 0 to time t
AUC(0-tlqc)	area under the plasma concentration-time curve from time 0 to time of last quantifiable concentration (tlqc)
AZA	azathioprine
BMI	body mass index
BSA	body surface area
CI	confidence interval
Cmax	maximum observed plasma concentration
CrCl	creatinine clearance
CS	clinically significant
CTCAE	Common Terminology Criteria for Adverse Events
CYC	cyclophosphamide
CYP	cytochrome P-450
DDI	drug-drug interaction
DLT	dose-limiting toxicity
dsDNA	double-stranded deoxyribonucleic acid
eCRF	electronic case report form
eGFR	estimated glomerular filtration rate
ECG	electrocardiogram
ESRD	end-stage renal disease
EOT	End of Treatment
ET	Early Termination
FACT	functional assessment of cancer therapy
FDA	Food and Drug Administration
FSH	follicle-stimulating hormone
GCP	Good Clinical Practice
GFR	glomerular filtration rate
GI	gastrointestinal
GN	Glomerulonephritis
HBsAg	hepatitis B surface antigen

hCG	human chorionic gonadotropin
HCV	hepatitis C virus
IB	Investigator's Brochure
ICH	International Conference on Harmonisation
IEC	independent ethics committee
Ig	Immunoglobulin
IgA	Immunoglobulin A
IgG	immunoglobulin G
IgM	immunoglobulin M
IRB	institutional review board
ISN	International Society of Nephrology
ISV	insufficient sample volume
IVRS/IWRS	interactive voice response system/interactive web response system
K2EDTA	dipotassium ethylenediamine-tetraacetic acid
LLN	lower limit of normal
LN	lupus nephritis
MedDRA	Medical Dictionary for Regulatory Activities
MMF	mycophenolate mofetil
MRD	multiple-rising dose
MTD	maximum tolerated dose
NCS	not clinically significant
NOAEL	no-observed-adverse-effect level
NSAID	nonsteroidal anti-inflammatory drug
PGx	pharmacogenomics
PK	pharmacokinetic(s)
PO	Orally
PT	preferred term
PTE	pretreatment event
QTcF	QT interval with Fridericia's correction method
RBC	red blood cell
Com pany Confidential Information	[REDACTED]
RPS	Renal Pathology Society
RRMM	relapsed refractory multiple myeloma
SAE	serious adverse event
SAP	statistical analysis plan
sCR	serum creatinine
SLE	systemic lupus erythematosus
Company Confidential Information	[REDACTED]
SNP	single nucleotide polymorphism
SOC	system organ class
SRC	Safety Review Committee

Com	[REDACTED]
pany	
TR	tuberculosis
Conf	
deni	
PLAE	treatment-emergent adverse event
al	
Tmax	time to reach Cmax
in	
meti	upper limit of normal
on	
CLN	
UPCR	urine protein to creatinine ratio
WBC	white blood cell
WHO	World Health Organization

4.0 OBJECTIVES

4.1 Primary Objective

To characterize the safety and tolerability of ixazomib when administered as multiple oral doses at escalating dose levels in subjects with lupus nephritis (LN).

4.2 Secondary Objective

- To assess changes from Baseline in urine protein to creatinine ratio (UPCR) in LN subjects following multiple administrations of ixazomib.
- To evaluate the effect of ixazomib on kidney function, as assessed by changes from Baseline in serum creatinine (sCR), and estimated glomerular filtration rate (eGFR).
- To evaluate the effect of ixazomib on anti-dsDNA antibody titers and complement C3/C4 levels.
- To characterize the plasma PK of ixazomib in LN subjects when ixazomib is administered over 3 cycles consisting of 3 doses per cycle.

4.3 Additional Objectives

Not applicable.

4.4 Study Design

See Protocol Section 6.

5.0 ANALYSIS ENDPOINTS

[figure not shown]
5.1.1 Primary Endpoint

- Percentage of study subjects with at least 1 Grade ≥ 2 treatment emergent adverse event (TEAE) according to CTCAE.
- Percentage of study subjects with at least 1 serious adverse event (SAE).
- Percentage of study subjects with at least 1 adverse event leading to discontinuation of investigational study medication.
- Percentage of subjects with at least 1 markedly abnormal laboratory criteria for hematologic parameters.

[figure not shown]
5.1.2 Secondary Endpoints

- Change from Baseline to Final Visit of treatment period in UPCR.
- Change from Baseline to Final Visit of treatment period in sCR level.
- Change from Baseline to Final Visit of treatment period in eGFR measurement.
- Change from Baseline to Final Visit of treatment period in levels of autoantibodies (anti-dsDNA) and complement (C3 and C4).
- Plasma PK of ixazomib in subjects with LN following administration of ixazomib.
 - Plasma PK endpoints will be the following PK parameters of ixazomib in all cohorts:
 - Maximum plasma concentration (C_{\max}).
 - Time to reach C_{\max} (T_{\max}).
 - Area under the plasma concentration-time curve from time 0 to the last quantifiable concentration ($AUC_{(0-t_{lq})}$); or $AUC_{(0-168)}$, if measurable.

5.1.3 Exploratory Endpoints

- Company Confidential Information
- 

Company Confidential Information

5.1.4 Additional Safety Endpoints

Other safety assessments include vital sign measurements, ECGs, physical examinations and clinical laboratory tests.

6.0 DETERMINATION OF SAMPLE SIZE

This study is not statistically powered for any hypothesis testing. The sample size of at least 4 active and 1 placebo subjects for each of the 0.5 mg and 2.0 mg dose groups (Cohorts A and B, respectively), 6 active and 2 placebo subjects for each of the 3.0 and 4.0 mg dose groups (Cohorts C and D, respectively) is considered to be sufficient to fulfill the study objectives of the evaluation of safety, tolerability, and pharmacokinetics of each cohort.

7.0 METHODS OF ANALYSIS AND PRESENTATION

7.1 General Principles

Continuous data will be summarized using the following descriptive statistics: number of subjects (N), mean, standard deviation (SD), median, minimum, and maximum, where appropriate. Where indicated, the coefficient of variation (%CV) and geometric mean will also be included in the summary of continuous data. Categorical data will be summarized using the number and percent of subjects for each category, where appropriate.

Unless otherwise stated, baseline value is defined as the last observed value before the first dose of study medication.

Subjects who receive placebo in each cohort will be pooled across the cohorts. All study-related raw data for randomized subjects will be presented in listings. All summaries will be presented by the pooled placebo group, ixazomib doses, ixazomib overall, and overall subjects in the study separately. All data analyses and figures will be generated using SAS System® Version 9.2 or higher.

7.1.1 Study Definitions

There are no study-specific definitions.

7.1.2 Definitions of Study Days

Study day will be calculated relative to the date of the first dose of the study drug. Study days prior to the first dose of study drug will be calculated as: {date of assessment/event – date of first dose of study drug of the subject}. Study days on or after the first dose of study drug will be calculated as: {date of assessment/event – date of first dose of study drug of the subject + 1}.

7.1.3 Definition of Study Visit Windows

There will be no visit windows.

7.1.4 Conventions for Missing Adverse Event Dates

There will be no imputation of incomplete, or missing adverse event dates.

7.1.5 Conventions for Missing Concomitant Medication Dates

There will be no imputation of incomplete, or missing concomitant medication dates.

7.1.6 Conventions for Missing Data

There will be no imputation of incomplete or missing data.

7.2 Analysis Sets

Safety Set:

The Safety Analysis Set will consist of all subjects who are enrolled and received at least 1 dose of study drug. Subjects in this analysis set will be used for demographic, baseline characteristics and safety summaries.

Pharmacokinetic Set:

The PK set will consist of all subjects who receive study drug and have at least 1 measurable plasma concentration.

Pharmacodynamic Set:

The PD set will consist of all subjects who receive study drug and have at least 1 postdose PD measurement.

7.3 Disposition of Subjects

Disposition of all screened subjects (denominator) will be tabulated (count and percent); there will be no inferential analysis of subject disposition data.

Summaries will be presented by the pooled placebo group, ixazomib doses, ixazomib overall, and overall subjects in the study.

Disposition of all randomized subjects will be tabulated for each part of the study:

- All subjects received at least one dose of study drug (denominator).
- Subjects who completed the study drug.
- Subjects who prematurely discontinued study drug.
- Subjects who completed all study visits.
- Subjects who prematurely discontinued study visits.

Primary reasons for discontinuation of study drug/visits, as entered on the electronic case report form (eCRF), will be tabulated. The date of first dose, date of last dose, duration of treatment and the reason for premature discontinuation of study drug/study visit will be presented for each subject in listings.

Primary reasons for failure will be summarized and will be presented in a data listing.

7.4 Demographic and Other Baseline Characteristics

Demographic and baseline characteristics will be summarized using the safety set by pooled placebo group, ixazomib doses, ixazomib overall, and overall subjects in the study.

Summary statistics will be presented for continuous variables (age, height, weight, and body mass index [BMI]). The number and percentage subjects within each category will be presented

for categorical variables (for example, gender, race, etc.). Individual subject demographic and baseline characteristic data will be listed.

Demographic variables of screen failure subjects and reasons for screen failures will be summarized overall for subjects who are screened but not enrolled in the study.

7.5 Medical History and Concurrent Medical Conditions

Medical history refers to the significant conditions or diseases relevant to the disease under study that resolved at or prior to signing of informed consent. Concurrent medical conditions are those significant ongoing conditions or diseases present at signing of informed consent.

Medical history and concurrent medical conditions will be coded using the latest version of Medical Dictionary for Regulatory Activities (MedDRA, version 20.0) will be presented in listings based on safety analysis set.

7.6 Medication History and Concomitant Medications

Medication history information to be obtained includes any medication relevant to eligibility criteria and the efficacy or safety evaluations stopped at or within 28 days before signing of informed consent. Medications used from signing of informed consent through the end of each study part will be considered as concomitant medications for each study part, respectively.

Concomitant medication is defined as the medication that the patient started taking before first dose and ongoing in the study. Missing, partial, incomplete date/time for concomitant medications won't be imputed; these will be listed as such.

All medication history and concomitant medications data will be presented in listing. This listing will be based on safety set.

7.7 Study Drug Exposure and Compliance

The date and time of each dose for each subject will be reported in a data listing.

Summaries of ixazomib PK concentration data will be provided (See Section 7.9.1). No other summary statistics for the extent of exposure to study drug or compliance calculations will be performed.

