7.9 Pharmacokinetic and Pharmacodynamic Analysis

7.9.1 Pharmacokinetic Analysis

7.9.1.1 Pharmacokinetic Concentrations

Individual subject plasma and Company Confidential concentration data for ixazomib will be listed for all subjects in the safety set. Both Scheduled and actual PK sample collection times will be presented in listings.

For the pharmacokinetic set, plasma and Company Confidential ixazomib concentration data will be summarized by time point for each ixazomib dosing cohort using descriptive statistics (N, mean, SD, %CV, median, maximum, and minimum). Summary statistics will be calculated by assigning a value of 0 to all values below the limit of quantification (BLQ).

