7.11.1 Adverse Events

A Pre-Treatment Event (PTE) is defined as any untoward medical occurrence in a clinical investigation subject who has signed informed consent to participate in a study, but prior to administration of any study medication; it does not necessarily have to have a causal relationship with study participation.

An AE is defined as any untoward medical occurrence in a clinical investigation subject administered a drug; it does not necessarily have to have a causal relationship with this treatment. PTE and AE verbatim terms will be coded by SOC and PT using MedDRA (version 20.0 or later).

Treatment-Emergent Adverse Events (TEAE)s will be defined as AEs that occur after the first dose of study drug received in the treatment period and up to 30 days (onset date – last date of dose + 1 ≤ 30) after the last dose of study drug or early termination.

TEAEs will be presented by severity (mild, moderate, and severe). Serious TEAEs, TEAEs leading to study drug discontinuation, and TEAEs leading to death will also be summarized using SOC and PT.

When calculating the frequency and percentage of subjects who reported TEAEs, a subject will be counted only once for each SOC or PT when multiple TEAEs are coded to the same SOC or PT. For the intensity or relatedness summaries, if a subject reports multiple TEAEs coded to the same SOC or PT, the TEAE with maximum intensity or strongest relationship will be included in the summary.

AEs with missing severity will be listed as such in the AE listings, however, will be summarized as severe in summary tables. Similarly, if the relationship of an event is missing, the event will be considered as related but in listings it will be presented as missing.

In general, AEs will be tabulated at the following levels: overall summary (subjects with at least 1 AE in any dose or treatment), the MedDRA SOC, and the MedDRA PT. The tables will

include the number and percentage (N[%]) of subjects. The following summary tables will be generated for all cohorts:

- Overview of Treatment-Emergent Adverse Events.
- Treatment-Emergent Adverse Events by System Organ Class and Preferred Term.
- Serious Treatment-Emergent Adverse Events by System Organ Class and Preferred Term.
- Most Frequent (>5% or N>2) Non-Serious Adverse Events by Preferred Term.
- Most Frequent (>5% or N>2) Non-Serious Adverse Events by System Organ Class and Preferred Term.

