7.13 Changes in the Statistical Analysis Plan

Only analysis on Cohort A and B, and Double-Blind treatment period of the study will be presented because study has been terminated early.

Due to the fact that the study was terminated before the finalization of this statistical analysis plan, no summaries nor analysis will be performed for the exploratory endpoints. Data collected on eCRF or from study procedures that are related to the exploratory endpoints will be listed if appropriate. Additionally, no PK parameters will be derived due to early termination of the study.

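### Does SAP 7.7 leave the safety percentages unreadable by ruling out a by-group table of doses received and treatment duration?

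*SAP*

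**What the plan says.** SAP 7.7 (Study Drug Exposure and Compliance) lists when each subject took each dose, refers to the concentration summaries in 7.9.1, and closes with: "No other summary statistics for the extent of exposure to study drug or compliance calculations will be performed". Under 7.9.1.1, "ixazomib concentration data will be summarized by time point for each ixazomib dosing cohort", so those summaries say nothing about placebo and do not count doses.

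SAP 7.3 (Disposition of Subjects) supplies the rest. By pooled placebo, ixazomib dose, all ixazomib and all subjects, it counts those who completed study drug and "Subjects who prematurely discontinued study drug", does the same for study visits, and tabulates the reasons for stopping. Together with the start of dosing, it promises the following: "date of last dose, duration of treatment and the reason for premature discontinuation of study drug/study visit will be presented for each subject in listings".

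SAP 7.13 limits the report: "Only analysis on Cohort A and B, and Double-Blind treatment period of the study will be presented because study has been terminated early". SAP 6.0 says that the study is not powered for any hypothesis test.

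**The concern.** The primary objective is safety over multiple doses. The primary endpoints in SAP 5.1.1 are all of the at-least-one-event kind, for example "Percentage of study subjects with at least 1 adverse event leading to discontinuation of investigational study medication". Such percentages tend to rise with the number of doses taken and the time observed. The population does not protect against unequal exposure: "The Safety Analysis Set will consist of all subjects who are enrolled and received at least 1 dose of study drug". A discontinued row in a disposition table does not separate a subject who stopped after one dose from one who stopped just before the last.

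The adverse event rule in SAP 7.11.1 adds to this. Events count as treatment-emergent if they occur "after the first dose of study drug received in the treatment period and up to 30 days" after dosing ends, so longer treatment also means a longer counting period. If early termination had cut the groups short to different degrees, two percentages could differ for that reason alone, and no summary table would show it.

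**Working it through.** The SAP states no figure to reproduce here. The check is what a by-group exposure table would add to what is already planned.

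**1. Number of subjects.** SAP 6.0 plans at least 4 active and 1 placebo subjects in each of Cohorts A and B:

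- active: 4 + 4 = 8
- pooled placebo: 1 + 1 = 2
- total: 8 + 2 = 10 (planned minimum; the SAP does not give the number actually treated)

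**2. Number of doses.** The pharmacokinetic objective in SAP 4.2 describes 3 cycles of 3 doses, so 3 × 3 = 9. This is an inference, because SAP 4.4 leaves the design to the protocol. On that reading the discontinued row can cover 1 to 8 doses, and the dosing listing has at most 10 × 9 = 90 entries at the planned minimum.

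**3. Where each item already appears.**

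| Item a table would give | Where the SAP already gives it |
|---|---|
| Doses received per subject | Dosing listing, 7.7 |
| First dose, last dose, duration | Listing, 7.3 |
| Reason for stopping | Listing and table by group, 7.3 |
| Completed or stopped study drug, placebo included | Table by group, 7.3 |
| Completed or stopped visits, placebo included | Table by group, 7.3 |

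Only the arithmetic summary of the first two rows is left out. With 2 placebo subjects, the minimum and maximum are the two listed values. With 4 subjects per ixazomib dose, median, minimum and maximum condense four values that are already printed.

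**4. Effect on the primary results.** Each primary endpoint is subjects with at least one event divided by subjects in the set. Neither count uses the number of doses or the duration as tabulated by group. The change in every percentage from adding the table is 0.

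**5. The counting window.** The bracketed formula in 7.11.1 is onset − last dose + 1 ≤ 30, hence onset ≤ last dose + 29 days. Counted from the first dose, the window is (last dose − first dose + 1) + 29 = duration + 29 days, or 1 + 29 = 30 days after a single dose. This follows from the formula only. The sentence around it names early termination as an alternative to the last dose, and if that is a separate anchor, a subject who stopped early could be counted for longer. So it is not established that duration alone fixes the window. In any case the dates are listed.

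**6. How much unequal exposure could matter.** With a per-dose event probability p and independent doses, P(at least one event in k doses) = 1 − (1 − p)^k. The values of p are assumptions and are not in the SAP.

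| p | 3 doses | 6 doses | 9 doses | ratio, 9 to 3 doses |
|---|---|---|---|---|
| 0.05 | 14.3% | 26.5% | 37.0% | 2.6 |
| 0.10 | 27.1% | 46.9% | 61.3% | 2.3 |
| 0.20 | 48.8% | 73.8% | 86.6% | 1.8 |

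This shows why exposure is relevant to reading such percentages. It does not show that the groups differed, since the SAP reports no difference and the contrast of 3 with 9 doses is hypothetical.

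**The case for a change.** The strongest case for the concern is that SAP 7.7 makes an explicit exclusion in the section meant for exposure, so it cannot be excused as silence that the protocol fills. SAP 7.13 cites early termination for dropping PK parameters and exploratory analyses, but nowhere gives a reason for leaving out exposure. Demographics, laboratory values and adverse events are summarised for the same few subjects, so small numbers do not by themselves explain the choice. Small groups also make each subject weigh heavily: 1/4 = 25 percentage points within an ixazomib dose, and 1/2 = 50 points in pooled placebo.

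Much of this stands as description. No section restores a by-group summary of doses or duration, no reason is given, and one short table would be cheap and convenient. But it does not turn the choice into a mistake. Where one subject moves a percentage by 25 or 50 points, a reader has to look at individual subjects anyway, and for that the listing of doses, dates and reasons is more informative than a median and a range.

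**Conclusion.** The concern does not hold. SAP 7.7 is deliberate, agrees with SAP 7.3 and contradicts nothing else in the document. All the information stays available: in listings for every subject, and in by-group counts of completion and discontinuation that include placebo. For a planned minimum of 10 subjects in a terminated, purely descriptive study, listing these values instead of summarising them is a defensible choice. No primary percentage changes.

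This conclusion assumes that the number analysed is near the planned minimum and that the listings in 7.3 and 7.7 are produced as described. It does not depend on whether 9 is the exact planned number of doses or on how the early-termination wording in 7.11.1 is read. A large number of subjects, or a documented exposure difference between groups, would give the request for a table more weight, but the SAP shows neither.

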7.8 Efficacy Analysis

Not applicable.

7.8.1 Primary Efficacy Endpoint(s)

Not applicable.

7.8.2 Secondary Efficacy Endpoint(s)

Not applicable.

7.9 Pharmacokinetic and Pharmacodynamic Analysis

7.9.1 Pharmacokinetic Analysis

7.9.1.1 Pharmacokinetic Concentrations

Individual subject plasma and Company Confidential concentration data for ixazomib will be listed for all subjects in the safety set. Both Scheduled and actual PK sample collection times will be presented in listings.

For the pharmacokinetic set, plasma and Company Confidential ixazomib concentration data will be summarized by time point for each ixazomib dosing cohort using descriptive statistics (N, mean, SD, %CV, median, maximum, and minimum). Summary statistics will be calculated by assigning a value of 0 to all values below the limit of quantification (BLQ).

7.9.1.2 Pharmacokinetic Parameters

No PK parameters will be derived due to early termination of the study.

7.9.2 Pharmacodynamic Analysis

All PD summaries will be based on the PD set.

7.9.2.1 Pharmacodynamic Concentrations

Pharmacodynamic measures will include hematologic measures of serum anti dsDNA antibody, other autoantibodies and complement C3/C4 levels. Samples will be collected as noted in Appendix A in the Protocol. These assays are routinely performed in the central laboratory.

Baseline value, final visit value, and change from baseline to final visit of the levels of autoantibodies (anti-dsDNA) and complement (C3 and C4) will be summarized by pooled placebo, ixazomib dose and ixazomib overall (N, mean, SD, median, minimum, and maximum). Individual data for each subject will be provided in the listing.

Company Confidential Information

For serum and urine cytokine samples, the values at each time point, change from baseline to each visit of the levels of each analyte, except analytes in which all values are below LLOQ, will be summarized by pooled placebo, ixazomib dose and ixazomib overall (N, mean, SD, median, minimum, and maximum). Individual data for each subject will be provided in the listing.

